
Sleep Assessment: Patients will wear an I-Button continuously from Day 8 of the Run-In Period to Day 5 of the Wash-Out period except during periods of bathing.

Visit Day 1: Informed Consent

The eligible volunteers will be asked to sign the informed consent after explanations of the study and after all their questions have been answered. Patients will be registered to the study after they have provided informed consent.

At the beginning of the run-in period, the new cohort of 40 patients will have a screening visit. In the screening visit inclusion and exclusion criteria will be accurately reviewed and constipation history assessed using the Rome IV criteria. Patients will be included who have been constipated for over 6 months, who have two or fewer complete spontaneous bowel movements per week unresponsive to milk of magnesia and requiring Miralax or another laxative, bulking agent, softener or suppository at least once weekly. Details relating to depression, anxiety, memory problems, hallucinations, loss of smell, voice difficulties and sleep patterns, thrashing and speaking out loud during sleep, swallowing difficulties and dyspepsia will be recorded. Patients will have a physical examination, their vitals will be checked and their past and present medical history as well as their medication intake will be reviewed. Baseline blood chemistry will be checked. Women with childbearing potential will have a negative pregnancy test to enter in the study and within 48 hours of each of the studies. After they have signed the consent form, participants will be scheduled for the study-days and entry into the randomization procedure. They will also be instructed as to the use of daily diaries and I-Buttons. BDI, PFS-16, NMSQ, PDHQ, RBDQ, PDSS, MMSE, UPDRS and Trail-making A and B, PAC-SYM and PAC-QOL will be administered. They will be given Sitzmarks capsules to take on Days 8, 9, and 10.

Day 8, Phone call Assessment of constipation severity off medication and of colonic transit

Daily stool diaries which they will have been filling in for a week will be reviewed and those

patients with two or fewer complete, spontaneous bowel movements per week will proceed to

Sitzmarks assessment. This will trigger shipment of study drug.

Sitzmarks procedure Days 8, 9, and 10:

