• The patient will self-administer the Sitzmarks capsule (contains 24 radiopaque markers; Konsyl Pharmaceuticals, Texas, USA) by mouth with water on Days 8,9, and 10 and will consume their usual diet during this period. The patient will abstain from using suppositories or enemas until they return on Day 11. An abdominal XR will be scheduled on Day 11

Day 11 – Site Visit 2

An abdominal XR will be obtained to determine the location and the extent of elimination

of the radiopaque markers. Patients who expel at least 80% (19 or more of the markers) have

grossly normal colonic transit. If remaining markers are scattered about the colon, the condition is

most likely hypomotility or colonic inertia. If remaining markers are accumulated in the rectum or

rectosigmoid, the condition is most likely functional outlet delay. Radiographs will be collected in

electronic format and subsequently analyzed in blinded manner by a centralized reader ([name] MD, and [name], MHA, Division of Gastroenterology and Hepatology, Mayo

Clinic). The patient will be given study medication (B) and a PAC-SYM and PAC-QOL to take

home. This will trigger randomization to treatment or placebo and to PK or no PK.

Day 14- Phone call

Patients will be asked to complete the PAC+SYM and PAC-QOL questionnaires. They

will be instructed to take the medication the following morning on an empty stomach and not to

eat anything for at least 60 minutes thereafter. Baseline complete, spontaneous bowel movements

(CSBM) will be calculated from the diaries at the 14 day phone call as CSBM/entries x

7.Baseline PAC-SYM and PAC-OOL and baseline ease of passage and consistency will also be

obtained at this time-point.

PERIOD 3.2 (Stage 2): Multiple doses

Safety, tolerability and pro-kinetic effect of orally administered multiple-dose ENT-01 in

Sentinel Group followed by Remaining Cohort

Cohort 2 (40 patients, of which 10 comprise the sentinel group):

Duration: 17-19 days

The purpose of this period is to demonstrate the continued pro-kinetic effect beyond that

of a single-dose, to confirm the effective pro-kinetic dose for each individual and to establish the

safety, tolerability and PK of multiple doses of ENT-01. A pro-kinetic dose is defined as the dose

that results in a spontaneous, complete stool on at least two of the three dosing days. Once the

pro-kinetic dose is established, and assuming there are no safety concerns, each patient will be

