Sitzmarks Capsule Distributions ²	X							X				
Reminder to Take Sitzmarks Capsules ³		X							X			

		Period 3.1 Run-In					Period 3.2 Multiple Dose		Period 4 Randomized Treatment			Period 5 Wash-Out	
	Day 1 Visit 1	Days 2-7, 9- 10, 12-13 Calls	Day 8 Call	Day 11 Visit 2	Day 14 Call	Days 1-13, 15-16 Calls	Day 14 Call	Day 1 Visit 3 ⁶	Days 2-5 Calls	Day 6 Visit 4	Days 1-7 Calls	Day 14 Visit 5	
Reminder to Take Sitzmarks Capsules ³		X							X				
Abdominal X-Ray				X						X			
Dispense I-Button ⁴	X												
PK Draws & LFT ⁵								X		X			
Phone Call		X	X		X	X	X		X		X		

¹For PK patients, vital signs taken pre-dose and 2 hours after dose. Blood pressure will be taken for all patients twice, first lying down and then after 5 minutes of sitting or standing from the recumbent position. All other vital signs will be measured after the patient has been resting in a sitting position for at least 5 minutes.

²Sitzmark capsules are dispensed to patients at Visit 1 with instructions to take one a day on Days 8, 9, and 10 of the Run-In period for the abdominal X-ray on Day 11. Patients will receive more Sitzmark capsules at Visit 3 with instructions to take one a day on Days 3, 4, and 5 of the Randomized Treatment period for the abdominal X-ray on Day 6.

³Subjects are reminded during the Day 7 call of the Run-In period and Day 2 call of the Randomized Treatment period to begin taking the Sitzmark capsules the following day to prepare for the abdominal X-ray on Day 11 of the Run-In period and Day 6 of the Randomized Treatment period.

⁴Patients will wear an I-Button continuously from Day 8 of the Run-In period to Day 5 of the Wash-Out period except during periods of bathing.

[figure not shown]
⁵PK samples are taken pre-dose and 1, 2, 4, and 8 hours post-dose. A sample for liver function tests will be taken with the 8-hour post-dose PK draw.

⁶Visit 3 occurs on the day before randomization in non-PK subjects.

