APPENDIX 8: I-BUTTON

The I-Button is a small rugged self-sufficient system that measures temperature and records the results in a protected memory section. The Thermochron I-Button DS1921H (Maxim Integrated, Dallas TX) used for skin temperature measurement. The I-Button DS1921H is regulated by Federal Communications Commission (FCC) as a class B digital radiofrequency device that is an unintentional radiator (i.e., CFR 47, Part 15, Subpart B), and conforms to the national standards tested under ANSI C63.4-2001. The I-Button is composed of a semiconductor temperature sensor, a real timer, a memory and a lithium battery, all enclosed in a 16-mm diameter by 6-mm thick cylinder. Manufacturing specifications include: temperature range from +15 to +46 °C, and 1 °C of accuracy with a precision of 0.125 °C. The memory (NV RAM) allows it to record up to 2048 values taken at regular intervals of 1 to 255 min. I-Buttons will be programmed to sample every 10 min, and attached to a double-sided cotton sport wrist band using Velcro®, with the sensor face of the I-Button being placed over the inside of the wrist, on the radial artery of the dominant hand. Subjects will remove and replace the data logger when necessary (i.e., to have a bath or shower). After the period of monitoring, the information stored in the I-Button will be transferred through an adapter (DS1402D-DR8, IDC, Spain) to a personal computer using I-Button Viewer v. 3.22© 1992–2005 Dallas Semiconductor MAXIM software provided by the manufacturer. The value of skin temperature assessment in sleep research is that the endogenous skin warming resulting from increased skin blood flow is functionally linked to sleep propensity (Sarabia et al., 2008; van Marken Lichtenbelt et al., 2006).

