The protocol dated 27 July 2017 was amended during the trial. And the protocol amendment was finalized on 02 February 2018. In this amendment, Stage 2 dose range is from 100 mg to 250 mg with an increment 25 mg for next higher dose. It also removed randomization period.

Except for the above changes, there were no other changes from protocol dated 27 July 2017

Table 1: Overall Study Design

Period 1	STAGE 1			STAGE 2A			Period 5
	Period 2.1	Period 2.2	Period 3.1	Period 3.2	Period 4	Period 5	
Run-in sentinel group (Cohort 1)	Single dose escalation sentinel group	Washout	Run-in (Cohort 2)	Identification of prokinetic dose using a 10 subject sentinel group followed by the remaining subjects	1:1 Randomization onto placebo or prokinetic dose	Washout	
2 weeks N=10	3 weeks N=10	2 weeks N=10	2 weeks N=40	≤17days N=40	6 days N=40	2 weeks N=40	

Table 2: Schedule of Assessments of Stage 1

Period	1 Run-In Sentinel 2 wks		2.1 Single Dose 3-8 wks	2.2 Wash-Out 2 wks
	D1	D14	D1	
Consent	X			
Demographics	X			
Inclusion/exclusion	X	X		
Medical history	X			
Physical exam	X		X	X
Vital signs ¹	X		X	X
Rome-IV	X			
Blood chemistry	X		X	X
Hematology	X			
Urinalysis	X			X
Fecal occult blood	X		X	X
EKG	X		X	X
Pregnancy test	X			
Monitoring			X	X
Discontinue medications	X			
Re-start medications				X
Diary entries	X	X	X	X
UPDRS	X		X ⁴	X ²
I-Button ³	X	X	X	
PAC-QOL	X	X	X ⁴	X ²
PAC_SYM	X	X	X ⁴	X ²
RBDQ	X		X ⁴	X ²
NMSQ	X		X ⁴	X ²
PFS-16	X		X ⁴	X ²
UM-PDHQ	X		X ⁴	X ²
BDI	X		X ⁴	X ²
Trail-making A and B	X		X ⁴	X ²

Table 2: Schedule of Assessment of Stage 1

Period	1 Run-In Sentinel 2wks		2.1 Single Dose 3-8 wks	2.2 Wash-Out 2 wks
	D1	D14		
MMSE	X		X ⁴	X ²
Adverse events		X	X	X
PK samples			X ⁵	
Schedule visit days	X			
Administer ENT Dose			X	
Record Medications	X	X	X	X
Daily phone calls to on non-visit days		X	X	X

¹Vital signs taken before dose and 2 hours after dose

²End of period 2

³I-Button placed days 9 of run-in periods and worn continuously through day 5 of wash-out periods.

⁴Surveys taken at last dosing visit

⁵PK samples taken pre-dose and 1, 2, 4, 8 and 24 hours post-dose

Table 3: Schedule of Assessments of Stage 2 under Protocol Dated 27 July 2017

Scheduled Assessments	Period 3.1 Run-In					Period 3.2 Multiple Dose		Period 4 Randomized Treatment			Period 5 Wash-Out	
	Day 1 Visit 1	Days 2-7, 9- 10, 12-13 Calls	Day 8 Call	Day 11 Visit 2	Day 14 Call	Days. 1-13, 15-16 Calls	Day 14 Call	Day 1 Visit 3 ⁶	Days 2-5 Calls	Day 6 Visit 4	Days 1-7 Calls	Day 14 Visit 5

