³Subjects are reminded during the Day 7 call of the Run-In period and Day 2 call of the Randomized Treatment period to begin taking the Sitzmark capsules the following day to prepare for the abdominal X-ray on Day 11 of the Run-In period and Day 6 of the Randomized Treatment period.

⁴Patients will wear an I-Button continuously from Day 8 of the Run-In period to Day 5 of the Wash-Out period except during periods of bathing.

⁵PK samples are taken pre-dose and 1, 2, 4, and 8 hours post-dose. A sample for liver function tests will be taken with the 8-hour post-dose PK draw.

⁶Visit 3 occurs on the day before randomization in non-PK subject

Table 4: Schedule of Events of Stage 2 under Protocol Dated 02 February 2018

Scheduled Assessments	Period 3.1 Run In					Period 3.2 Dose Escalation		Period 4 Fixed Dose		Period 5 Wash Out		
	Day 1 Visit 1 Screening	Days 2-7, 9,10,12,13 Phone Calls	Day 8 Phone Call	Day 11 Visit 2	Day 14 Phone Call	Days 1-13 Phone Calls	Day 14 Phone Call	Days 1-3 Phone Calls	Day 4 Visit 3	Days 1-7 Phone Calls	Day 14 Visit 4	Day 28 FU Call
Informed Consent	X											
Inclusion/Exclusion Criteria	X											
Demographics/Medical History	X											
Concomitant Medications	X	X	X	X	X	X	X	X	X	X	X	
Complete Physical Exam	X											X
Height	X											
Weight	X			X					X		X	
Vital Signs (1)	X			X					X		X	
EKG	X								X		X	
Local Labs: Chemistry*, Hematology*	X								X		X	
Local Labs: Coagulation Panel*	X											
Local Labs: Serum Pregnancy (2a) or FSH (2b)	X											
Urinalysis* (dipstick)	X								X		X	
Urine Pregnancy Test (3)				X					X		X	
Fecal Occult Blood (4)	X								X		X	
Study Drug Dispense, Accountability, Collection				X					X			
Reminder to Begin Taking Study Drug the Next					X							
Instruction to Discontinue Laxatives and Other Restricted Medications (5)	X											
Instruction to Resume Laxatives and Other Restricted Medications										X (6)		
Stool and Sleep Diary Instruction/Review	X	X	X	X	X	X	X	X	X	X	X	
AE Assessment and Review	X	X	X	X	X	X	X	X	X	X	X	X
Rome IV Questionnaire	X		X									
UPDRS	X								X		X	
PAC-QOL and PAC-SYM	X				X		X		X		X	
BDI-II, NMSQ, PFS-16, UM-PDHQ, MMSE, Trail-Making A and B, RBDQ, PDSS	X								X		X	
I-Button	X (7)		X						X (9)	X (10)		

* Refer to Appendix 1 for full list of clinical laboratory assessments

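### At 10-minute sampling the I-Button holds 14.2 days, but 2017 Stage 2 completers wear it for 23–37 days with no interim download, so one recording cannot span the periods of the exploratory temperature comparison

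*Protocol*

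**What the plan says.** Appendix 8 of the protocol gives the device's limit and its setting together: the memory can "record up to 2048 values taken at regular intervals of 1 to 255 min. I-Buttons will be programmed to sample every 10 min". On retrieval it says "After the period of monitoring, the information stored in the I-Button will be transferred" to a computer through an adapter. It then plans to compare daily temperature rhythm at baseline with that under treatment.

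For Stage 2, Period 3.1 in protocol Section 3 states: "Patients will wear an I-Button continuously from Day 8 of the Run-In Period to Day 5 of the Wash-Out period". Footnote 4 of the Stage 2 schedule in Appendix 2 repeats this. That schedule has one device row, "Dispense I-Button", marked only at Visit 1. For Stage 1, footnote 3 of the Stage 1 schedule has the device placed on run-in Day 9 and worn continuously through wash-out Day 5.

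Period 3.2 is headed "Duration: 17-19 days", while the period table in Section 3 caps it at 17 days. The February 2018 protocol is not among the documents. SAP Section 2.1 summarises it: "In this amendment, Stage 2 dose range is from 100 mg to 250 mg with an increment 25 mg". It also removes randomization. SAP Table 4 prints "Period 3.2 Dose Escalation" over 14 days, followed by 4 fixed-dose days. Device wear still ends on wash-out Day 5.

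No schedule in either document shows an interim read-out, re-start or replacement. SAP Section 7.8.8 leaves I-Button data to a separate group.

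**The concern.** Memory and sampling interval together fix how long a single recording can last, and the wear schedules run well past that. The planned contrasts need data from both ends of the wear period. Appendix 8 needs baseline and treatment. The exploratory analyses in protocol Section 10.5 need change to the end of Period 3.2 and an arm comparison at the end of Period 4. A recording that fills or overwrites part-way removes one end. Patients would wear a device for weeks while much of what it measured was not kept. Protocol Section 2.2 makes the device the objective surrogate for sleep onset, awake periods and circadian rhythm.

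**Working it through.** **Check on period lengths.** Section 11 of the protocol gives at most 25 Stage 2 dosing days. Five levels (75–175 mg, SAP Section 2.1) × 3 days + 4 fixed-dose days + 6 randomized days = 25, which reproduces it. Period 3.2 at full escalation is then 15 + 2 to 15 + 4 = 17–19 days. Its minimum is 3 + 2 = 5 days. In Stage 1, eight doses 3–7 days apart span 1 + 7×3 = 22 to 1 + 7×7 = 50 days for one patient. The 57 in the Period 2.1 heading is the staggered cohort calendar.

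**Capacity.** 2,048 × 10 / 1,440 = 14.2 days (144 readings a day).

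**Continuous wear, completers.**

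| Schedule | Days | Readings at 10 min | Share covered |
|---|---|---|---|
| Stage 2, 2017, shortest | 7 + 5 + 6 + 5 = 23 | 3,312 | 62% |
| Stage 2, 2017, Period 3.2 of 17 days | 7 + 17 + 6 + 5 = 35 | 5,040 | 41% |
| Stage 2, 2017, longest | 7 + 19 + 6 + 5 = 37 | 5,328 | 38% |
| Stage 1, shortest | 6 + 22 + 5 = 33 | 4,752 | 43% |
| Stage 1, longest | 6 + 50 + 5 = 61 | 8,784 | 23% |

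For 2018, from the SAP summary only and assuming that 3 days per level and at least 2 fixed-dose days carry over:
- shortest: 7 + 3 + 2 + 5 = 17 days (84% covered);
- as printed: 7 + 14 + 4 + 5 = 30 days (47%);
- all seven levels from 100 to 250 mg: 7 + 21 + 4 + 5 = 37 days (38%).

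**What survives in Stage 2, 2017.** The documents do not say when logging starts or what happens when memory is full, so each case is shown.

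- *Starts on run-in Day 8, stops when full.* 14.2 − 7 = 7.2 days from first dose. A first-level responder's Period 3.2 (5–7 days) fits, leaving 2.2 to 0.2 days of Period 4. A second-level responder needs at least 6 + 2 = 8 days, so the end of Period 3.2 is already cut. Wash-out is lost for all.
- *Armed at dispensing on Day 1, stops when full.* 14.2 − 14 = 0.2 dosing day.
- *Overwrites, ended at wash-out Day 5.* The shortest wear loses 23 − 14.2 = 8.8 days, more than the 7 baseline days, so no completer keeps a baseline. What remains is wash-out, Period 4 and the last 14.2 − 5 − 6 = 3.2 days of Period 3.2.
- *Overwrites, runs on to Visit 5 (wash-out Day 14).* 14.2 − 13 = 1.2 randomized days at most.

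**Other wear instructions, on one recording.**
- Five-day blocks in four periods (Section 2.2): 20 days, 2,880 readings.
- Start at the lowest dose (Period 3.2): 5 + 6 + 5 = 16 to 19 + 6 + 5 = 30 days, with no baseline.
- Five run-in days, then all dosing and randomized days and five wash-out days (Section 9.2): 21–35 days.

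None fits 14.2 days.

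**The case against.** The transfer sentence in Appendix 8 does not say that one recording must span every period. If the five-day blocks of Section 2.2 were recorded and downloaded separately, each would need only 720 readings. The separate group may have a device procedure that covers this, and Stage 1 patients attend clinic for every dose, so a read-out there is easy. This is fair, but no such step is written, and both Period 3.1 and the schedule footnotes require continuous wear. As written, the plan does not fit the device.

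Two parts of the objection limit the point. A reader might infer that the baseline-versus-treatment comparison is lost for everyone. It is not: with a Day 8 start and stop-when-full, baseline versus end of Period 3.2 survives for patients who respond at the first dose level. Under the shortest 2018 course only 17 − 14.2 = 2.8 days are lost. A reader might also take the Stage 1 shortfall as an endpoint failure. The synopsis lists the I-Button under Stage 2, Section 2.1 names no I-Button endpoint, and Section 10.5 refers only to Stage 2 periods. Only the general wording of Appendix 8 could reach Stage 1.

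**Conclusion.** The point holds, within limits. One 14.2-day recording cannot cover baseline, dosing, randomized and wash-out periods when 2017 wear is 23–37 days in Stage 2 (35 at most if Period 3.2 is capped at 17 days) and 33–61 days in Stage 1. The capacity and wear arithmetic is firm. Which data are lost is conditional on the unstated start time and full-memory setting. The figures apply to completers; patients who stop early may fit. The 2018 figures rest on the SAP's summary alone.

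The documents do not support reading this as a threat to the trial's conclusions. Only an exploratory measure is affected, mainly in Stage 2. No primary or safety result depends on it, and the SAP's own sleep parameters come from the diary (Section 4.4.2). It should be corrected because the correction is cheap and lost readings cannot be recovered.

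**What to change.** Amend Appendix 8 as follows.

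- **One interval per patient.** Use the same interval for every recording of a patient, so that baseline and treatment have equal resolution.
- **Stage 2.** Download and re-arm at Visits 2 and 3. The longest 2017 gap, Visit 2 (run-in Day 11) to Visit 3, is 3 + 19 = 22 days, or 23 for PK patients. It needs at least 23 × 1,440 / 2,048 = 16.2 min. At 20 min capacity is 28.4 days, and the 23-day gap takes 1,656 readings. The other gaps also fit: Day 1 to Visit 2 is 10 days (720), and Visit 3 to Visit 5 is at most 21 days (1,512). For 2018 the printed gap is 3 + 14 + 4 = 21 days (1,512). If all seven levels are used it is 28 days (2,016), leaving 32 readings or 10.7 hours, so allow a slightly longer interval there.
- **Stage 1.** Download at each dosing visit. If armed on Day 1, use 20 min throughout: the run-in recording is up to 21 days for subjects 3–10 if they run in alongside subjects 1–2 (1,512 readings), dosing gaps are up to 7 days (504), and the last recording is 15 days if it runs to the Day 14 visit (1,080). If logging starts on run-in Day 9 and stops when full, 10 min throughout works: the run-in recording is 6–13 days (864–1,872) and dosing gaps take up to 1,008. The last recording would reach 2,160 readings by Day 14, but it fills only after the five wash-out wear days.
- **State the settings.** Give the logger start time and whether it stops or overwrites when full.
- **Reconcile the wear instructions** in Sections 2.2, 3.1 (Periods 3.1 and 3.2) and 9.2 and both schedules in Appendix 2, and the two statements of Period 3.2's length.

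Cost: a setting within the stated 1–255 min range and a brief download at visits already planned, with the adapter and computer available at sites. No extra visit or logger is needed. The downside is resolution: a 30-minute awakening gives 1–2 readings at 20 min instead of 3. Keeping 10 min in Stage 2 and swapping loggers at Visits 2 and 3 would not work alone, because the 22–23 day gap exceeds 14.2 days.

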APPENDIX 9: NON-MOTOR SYMPTOMS QUESTIONNAIRE (NMSQ)

Have you experienced any of the following in the last month?

		Yes	No			Yes	No
1	Dribbling of saliva during the daytime.			16	Feeling sad, 'low' or 'blue'.		
2	Loss or change in your ability to taste or smell.			17	Feeling anxious, frightened or panicky.		
	Difficulty swallowing food or drink or problems with choking.			18	Feeling less interested in sex or more interested in sex.		
4	Vomiting or feelings of sickness (nausea).			19	Finding it difficult to have sex when you try.		
5	Constipation (less than three bowel movements a week) or having to strain to pass a stool.	s 		20	Feeling light-headed, dizzy or weak standing from sitting or lying.		
6	Bowel (faecal) incontinence.			21	Falling.		
7	Feeling that your bowel emptying is incomplete after having been to the toilet.			22	Finding it difficult to stay awake during activities such as working, driving or eating.	s 	
8	A sense of urgency to pass urine makes you rush to the toilet.			23	Difficulty getting to sleep at night or staying asleep at night.		
9	Getting up regularly at night to pass urine.			24	Intense, vivid or frightening dreams.		
10	Unexplained pains (not due to known conditions such as arthritis).			25	Talking or moving about in your sleep, as if you are 'acting out' a dream.		
11	Unexplained change in weight (not due to change in diet).			26	Unpleasant sensations in your legs at night or while resting, and a feeling that you need	_	_
12	Problems remembering things that have happened recently or forgetting to do things.			27	to move. Swelling of the legs.		
13	Loss of interest in what is happening around you or in doing things.				Excessive sweating. Double vision.		
14	Seeing or hearing things that you know or are told are not there.			30	Believing things are happening to you that other people say are not.		
15	Difficulty concentrating or staying focussed.						

